2 STUDY OBJECTIVES

2.1 Primary Objective

The primary objective of this clinical study is to evaluate the complete remission (CR) rate with SGN-35/AVD sequential therapy in patients ≥ 60 years old with untreated Hodgkin lymphoma (HL).

2.2 Secondary Objectives

The secondary objectives of this study are to:

- a) To examine the ORR, CR rate, and prognostic relevance of FDG-PET following 2 cycles of SGN-35.
- b) To evaluate the safety of sequential SGN-35/AVD/SGN-35 therapy.
- c) To determine the 2-year progression-free survival (PFS), time to treatment failure (TTF), freedom from progression (FFP), and overall survival (OS) rates following SGN-35/AVD sequential therapy.
- d) To evaluate patient-reported outcomes at baseline and during treatment to determine potential symptom palliation (of baseline/pre-treatment symptoms), treatment-related symptoms, and overall health-related quality of life (HRQL).
- e) To examine the association between baseline and end-of-treatment patient co-morbidities as assessed by the Cumulative Illness Rating Scale (CIRS) with outcome (CR, TTF, FFP, PFS, and OS) and toxicity.
- f) To collect peripheral blood for proposed future studies of tumor and host characteristics that may predict for clinical outcome and enhance existing prognostic indices.

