9. Combined PET/CT scan will be sufficient if the PET/CT is performed with oral contrast (intravenous contrast is encouraged, but not mandatory); if PET/CT is without oral contrast, then separate/dedicated CTs of chest/abdomen/pelvis (in addition to PET/CT) must be obtained. Please see Section 6.6 for further guidelines on recommended interpretation of PET scans.				
10. The first 22 evaluable patients entered on the study will have a repeat FDG-PET after the 2 "lead in" cycles of SGN35. This should be completed the week prior to planned initiation of AVD chemotherapy. All patients entered on study will have FDG-PET and CTs performed prior to day 1 of cycle 4 of AVD therapy (after day 15 of cycle 3). Thereafter, once a patient enters complete remission (CR), then only CT's (chest/abdomen/pelvis) should be obtained (not both PET/CT and dedicated CTs). All patients will have re-staging scans performed at the end of AVD chemotherapy (i.e., prior to start of SGN35 consolidation therapy).				
11. See Appendix III and Appendix IV for further details/methods for completion. This includes Co-morbidity assessment (Appendix III) and Activity of Daily Living (ADL) assessment (Appendix VI). Obtain once at baseline (pre-treatment) and then repeat once at the completion of all therapy.				
12. See Section 6.9 for exact timing and description and Appendix IV for Quality of Life forms.				
13. 30 days (+/- 2 days) after the last dose of treatment, patients should have repeat re-staging CTs +/- FDG-PET completed. Thereafter, the follow-up schedule will be office visits with blood tests q 3 months and re-staging CTs q 6 months for 3 years, then per local institutional guidelines. Patients who stop treatment early due to AEs or PD will also follow this schedule.				
14. See Table 4 in Section 12.3.3 for full explanation of which blood tubes (i.e., ACD/yellow, EDTA/purple, and red top) and timing (e.g., baseline/pre-SGN35, after 2 cycles of SGN35 lead-in, and after completion of AVD chemotherapy) of correlative blood studies.				

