- 9.3.2 The primary endpoint of the phase II portion of this study is the complete remission (CR) rate among older patients with Hodgkin Lymphoma receiving sequential SGN-35 therapy with adriamycin, vinblastine, and dacarbazine chemotherapy (S-AVD). This CR rate for the primary endpoint will be assessed at the completion of AVD chemotherapy (i.e., prior to SGN35 consolidation). Patients who are deemed 'chemotherapy intolerant' (i.e., do not complete 6 cycles of AVD chemotherapy) and have achieved a PR or CR may continue to SGN35 consolidation. Of note, all patients will be 'counted' towards the primary objective of CR rate at the end of AVD chemotherapy on an intent-to-treat basis. Patients who are designated chemotherapy intolerant (i.e., stop AVD chemotherapy prematurely), will have their remission rate analyzed for the primary objective at the time of stopping chemotherapy. These patients will still be followed for other/secondary study endpoints.
- 9.3.3 A true CR rate of 70% would be considered promising in this population, whereas a true complete response (CR) rate of 50% would not be

considered worthy of further study. A two-stage Simon optimal design will be used with 22 patients (21 evaluable patients who are eligible and begin protocol therapy) in the first stage and 26 patients (24 evaluable patients who are eligible and begin protocol therapy) in the second stage. Maximal type I error = 0.05, type 2 error = 0.2.

- 9.3.3.1 If 12 or more CRs are observed in the first stage among the 21 evaluable patients, accrual will continue to the second stage (n=24 evaluable patients in the 2nd stage of the Simon 2-stage).
- 9.3.3.2 If the 21st evaluable patient has enrolled to this study and fewer than 12 CRs have been observed/confirmed, then subsequent accrual to the study will be suspended for lack of adequate response. Once 12 CRs have been confirmed, then the trial may proceed (re-open to accrual if suspended) to the 2nd stage of the Simon 2-stage trial.
- 9.3.3.3 This treatment will be considered promising for further study if 27 or more of the 45 evaluable patients demonstrate CR.

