9.10.1 Although the study is designed as two-stage optimal design study for effectiveness outcome = percent CR rate, QoL analysis will also be powered to show reasonable QoL effect. From literature we gather that functional well being measures have an SD = 6, while FACT-G has SD=16. Looking at After-Before measures, with correlation = 0.5 and equal SD's, for a null hypothesis of no difference between After and Before, and a two sided alternative hypothesis, at $\alpha=5\%$, with $n=21$ patients in the first stage, we have 69% power to reject the null hypothesis in favor of alternative = 9 points for FACT-G. Similarly, if the study goes into second stage, $n=42$ patients gives 82% power to reject H_0 in favor of H_1 if the observed difference is 7 points for FACT-G. Similar results hold for functional well being measures.

9.11 Co-Morbidity assessment.

9.11.1 We will collect the number of co-morbidities for each patient at baseline and at the end of completion of all therapy utilizing the Cumulative Illness Rating Scale and assess the relationship between CIRS score and outcome (CR, DFS, PFS).

The comprehensive geriatric assessment (CGA) has been developed as a procedure to assess the objective health status of elderly persons.⁵²⁻⁵⁵ The CGA is considered to be more effective than standard medical evaluation for the care of the elderly. Initially, use of a CGA was based on its ability to predict morbidity and mortality in the general geriatric population, although accumulating data show the benefits of using the CGA specifically in patients with cancer.^{53,54,56} Comorbidity is an essential part of the CGA. Several comorbidity scales have been used in research, although the Cumulative Illness Rating Scale (CIRS) is one of the more prominent tools utilized in geriatrics.^{53,57} The CIRS measures chronic medical illness burden while taking into account the severity of chronic diseases. The CIRS has been revised to reflect common problems of elderly people and was renamed the Cumulative Illness Rating Scale for Geriatrics (CIRS-G);⁵⁸ this version has subsequently been validated.⁵⁹ Furthermore, several recent cancer related studies have validated the relevance of the CIRS to define comorbidities among oncology patient populations, some of which correlated with survival.^{60,61}

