14.2 APPENDIX II

DATA FOR FDG-PET/CT SCAN

Patient's initials: _____

Patient's study number: _____

Hospital name: _____

Date of PET scan: _____

Timing of PET (circle): baseline s/p SGN-35 lead-in s/p 3 cycles AVD s/p 6 cycles AVD

RESULT OF PET-CT SCANS according to 5-point scale:

1 : no uptake

2 : uptake \leq mediastinum

3 : uptake > mediastinum but \leq liver

4 : uptake > liver at some sites even if uptake \leq liver or mediastinum at other sites

5 : uptake > liver in > 90% of initial sites or development of new sites consistent with progressive disease

Score	1	2	3	4	5 (please circle)
--------------	----------	----------	----------	----------	--------------------------

List sites of residual uptake (score 4 and 5):

.....

.....

.....

Comments e.g. positive sites elsewhere in the body:

Name:..... Date:

Signature:

14.3 APPENDIX III**Modified Cumulative Illness Rating Scale (CIRS)****The Modified Cumulative Illness Rating Scale (CIRS).**

Body system	Score				
1. Cardiac (heart only)	0	1	2	3	4
2. Hypertension (rating is based on severity; organ damage is rated separately)	0	1	2	3	4
3. Vascular (blood, blood vessels and cells, bone marrow, spleen, lymphatics)	0	1	2	3	4
4. Respiratory (lungs, bronchi, trachea below the larynx)	0	1	2	3	4
5. EENT (eye, ear, nose, throat, larynx)	0	1	2	3	4
6. Upper GI (esophagus, stomach, and duodenum; pancreas; do not include diabetes)	0	1	2	3	4
7. Lower GI (intestines, hernias)	0	1	2	3	4
8. Hepatic (liver and biliary tree)	0	1	2	3	4
9. Renal (kidneys only)	0	1	2	3	4
10. Other GU (ureters, bladder, urethra, prostate, genitals)	0	1	2	3	4
11. Musculo-skeletal-integumentary (muscle, bone, skin)	0	1	2	3	4
12. Neurological (brain, spinal cord, nerves, do not include dementia)	0	1	2	3	4
13. Endocrine-Metabolic (includes diabetes, thyroid; breast; systemic infections; toxicity)	0	1	2	3	4
14. Psychiatric/Behavioral (includes dementia, depression, anxiety, agitation/delirium, psychosis)	0	1	2	3	4

PHILOSOPHY AND DEVELOPMENT OF THE SCALE

Compiling and quantifying medical problems in the elderly population will allow meaningful comparison of medical burden and treatment outcomes in elderly patients with variable and complex medical problems.

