- 4. Functional blindness/deafness: unable to read, recognize a familiar face, unable to conversational heading, even if “organically” he is not completely blind or deaf; laryngectomy (every cause, especially malignancies); required surgical intervention for vertigo; aphonia secondary to laryngeal impairment.

UPPER GASTROINTESTINAL SYSTEM

This category is comprehensive of the intestinal tract from esophagus to duodenum, and pancreatic trees: dysphagia, GERD, hiatal hernia, esophageal diverticula, any type of gastritis (consider also H. Pylori eradication or not), gastric/duodenal ulcer, acute or chronic pancreatitis, malignancies (comprehensive of gastric lymphoma).

Pay attention that type 1 diabetes is rated under “metabolic”.

- 0. No problem
- 1. Hiatal hernia, GERD or gastritis requiring prn meds; previous ulcer (>5 years ago); previous H. Pylori eradication therapy (>5 years ago)
- 2. Daily proton pump inhibitor/anti-acid meds; documented gastric or duodenal ulcer or H.P. eradication therapy within 5 years

3. Active gastric or duodenal ulcer; positive fecal occult blood test; any swallowing disorder or dysphagia; chronic pancreatitis requiring supplemental pancreatic enzymes for digestion; previous episode of acute pancreatitis
4. Any type of malignancies (see “*Rating Malignancies*”); previous gastric surgery because of cancer; history of perforated ulcer (gastric surgery not because of cancer, ulcerocele); melena/heavy bleeding from upper GI source; acute pancreatitis

LOWER GASTROINTESTINAL SYSTEM

Comprehensive of the rest of the G.I. system, from small bowel to anus: Whipple’s disease, diverticulosis, irritable bowel, malignancies. Constipation is rated, too, by type and frequency of laxatives required, or by history of impaction.

0. No problems, previous appendectomy, previous hernia repair (without complications)
1. Constipation managed with prn meds; active hemorrhoids; intestinal hernia requiring surgery; previous hernia repair with complications (intestinal adhesions, laparocoele, etc.); irritable bowel syndrome (few symptoms)
2. Constipation requiring daily bulk laxatives (psyllium, polycarbophil, sterculia, guar gum, etc.), or stool softeners; diverticulosis (previous diverticulitis); inflammatory bowel disease in remission with meds (>5 years ago)

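### Objective 2.2(e) relates end-of-treatment CIRS to outcome, but that score comes after CR is fixed and 9–10 months after the time-to-event clocks start; Section 9.11 does not say which CIRS is used

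*Combined protocol and SAP*

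**What the plan says.** Section 2.2(e) sets the objective "To examine the association between baseline and end-of-treatment patient co-morbidities as assessed by the Cumulative Illness Rating Scale (CIRS) with outcome", and lists the outcomes as "CR, TTF, FFP, PFS, and OS) and toxicity". Both scores, baseline and end of treatment, are therefore on the explanatory side.

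Section 9.11.1 collects CIRS at the same two times and plans to "assess the relationship between CIRS score and outcome (CR, DFS, PFS"). It does not say which score is meant. It omits TTF, FFP, OS and toxicity, and it adds DFS, which the plan does not define. The methods that follow are logistic regression for CR, and Kaplan-Meier, log-rank and Cox models for time-to-event outcomes. There is no landmark, no time-dependent covariate and no restriction to the baseline score.

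On timing, footnote 11 to Table 4 (Section 7) reads "Obtain once at baseline (pre-treatment) and then repeat once at the completion of all therapy". Appendix VIII places the second form at the end of consolidation. For CR, Section 9.3.2 states "This CR rate for the primary endpoint will be assessed at the completion of AVD chemotherapy (i.e., prior to SGN35 consolidation"), and patients who stop AVD for intolerance "will have their remission rate analyzed for the primary objective at the time of stopping chemotherapy". OS, PFS, TTF and FFP all run from study entry (Sections 9.7 to 9.9).

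**The concern.** A predictor should be known before the outcome it is meant to predict. The final CIRS is recorded after CR has been decided. It is also recorded well into the follow-up of endpoints whose clocks started at entry, and its date depends on how treatment went. Part of what it counts may be harm from the treatment itself.

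An analyst following 2.2(e) literally could report that high comorbidity goes with failure when toxicity, or failure itself, produced the higher score. Section 1.8 explains why this matters: it hopes that objective criteria predicting morbidity and mortality might guide regimens or dosing in older patients, and asks for prospective evidence. Only a score taken before treatment can provide that.

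**Working it through.** **1. Nominal timeline** (day 0 = first SGN-35 dose; Sections 5.1, 5.3.1, 5.3.2 and 5.4.2.1; no delays)

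- End of lead-in: 2 × 21 = day 42.
- Last AVD dose: 42 + 5 × 28 + 14 = day 196. End of AVD cycle 6: 42 + 6 × 28 = day 210.
- First consolidation dose: 196 + 14 = day 210. Last: 210 + 3 × 21 = day 273.
- End of the last consolidation cycle: 273 + 21 = day 294. 30-day visit: 273 + 30 = day 303.

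Completion of all therapy is thus somewhere in days 273–303, about 9–10 months after the start. CR is fixed at about day 210. The gap is 273 − 210 = 63 to 303 − 210 = 93 days, or 2–3 months.

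**2. PFS events before the second CIRS**

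Section 9.3.5 assumes exponential PFS with a 2-year rate of 45% or 65%. With λ = −ln(S₂)/2, the median is ln 2/λ:

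- 65%: λ = 0.2154 per year, median 3.22 years (plan: 3.2).
- 45%: λ = 0.3993 per year, median 1.74 years (plan: 1.7).

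The plan's medians are reproduced. The fraction with an event by time t is 1 − exp(−λt):

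| 2-year PFS | Day 273 (0.747 y) | Day 294 (0.805 y) | Day 303 (0.830 y) | Of 45 patients |
|---|---|---|---|---|
| 65% | 14.9% | 15.9% | 16.4% | 6.7–7.4 |
| 45% | 25.8% | 27.5% | 28.2% | 11.6–12.7 |

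**3. What happens to those patients' scores**

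Patients without CR or PR after AVD go off study (Section 5.3.5), and progression is a reason to stop treatment (Section 10.5). Under footnote 11 their second CIRS comes early or after failure; under Appendix VIII they may have none. For TTF the link is tighter: stopping treatment for any reason is itself the event (Section 9.9.1), so in those patients the event sets the date of the score.

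**4. What the scale counts** (Appendix III)

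- The neurological category includes neuropathies of any cause.
- The upper gastrointestinal category gives level 4 for "melena/heavy bleeding from upper GI source; acute pancreatitis", and level 3 for a previous episode of acute pancreatitis. Documented prior pancreatitis is an exclusion (Section 3.3.8), so such a score at the end of treatment would normally reflect an on-study event.
- The respiratory category gives level 3 or 4 for acute pneumonia, depending on hospitalisation.

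Neuropathy, pancreatitis and lung infection are all listed side effects of SGN-35 (Section 8.1.11). The guide has no rule excluding treatment-emergent conditions.

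**5. Illustration for CR** (assumed inputs, none from the plan)

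Take 45 patients with baseline CIRS Poisson with mean 5 and no effect of baseline CIRS on CR. Toxicity occurs in 30% and adds k points to the final score; CR is 75% without toxicity. A logistic test of CR on final CIRS at the 5% level rejects as follows:

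- k = 1–2, CR 50% with toxicity: about 6–11% by likelihood-ratio test (Wald 5–8%); more if CR falls further.
- k = 3–4, CR 35–50% with toxicity: about 12–39%, depending on scenario and test.
- k = 2–3, CR 65% with toxicity: about 5%.

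The baseline score stays near 5%.

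**The case against.** Several points on the other side stand.

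- A reader might take the label of CIRS item 13, "Endocrine-Metabolic (includes diabetes, thyroid; breast; systemic infections; toxicity"), as proof that the scale counts drug toxicity. It is not: the guide explains that part of the category as poisoning by metals, pesticides or carbon monoxide.
- The overlap with toxicity is partial. A healed pneumonia without sequelae scores 0. Neuropathy is named in its category but not in any level descriptor. Cytopenias share a category with haematological malignancy, which scores 4, and only the worst problem per category counts. They add nothing while the lymphoma is scored there, so I do not rely on them.
- A reader might take the simulated rates as the plan's false-positive rate. They are not. The simulation builds in a toxicity effect on both score and CR, so it shows how often that induced association would be detected. With small shifts or a weak effect on CR, little happens.
- A reader might infer immortal-time bias in every Cox model. If all scored patients reach the score at about the same time without an event, the hazard ratio is essentially that of a landmark analysis. The problem lies mainly with patients who fail early, or are scored early or after progression, and its effect on the hazard ratio has not been quantified.
- Section 9.11.1 does not itself call the final CIRS a predictor. It leaves the choice open; the commitment is in 2.2(e).

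None of this answers the order of events for CR, or supplies the missing specification in 9.11.

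**Conclusion.** The concern holds in limited form. For CR, and for toxicity or time-to-event outcomes that precede the second CIRS, the association in 2.2(e) runs backwards in time. For later events, the fault is a post-baseline covariate used with a clock that starts at entry. For toxicity, the association is also partly circular, to the extent that a toxicity persists or leaves a scored history.

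The firm sizes are the 2–3 month lag behind CR, and the 15–16% to 26–28% of patients with a PFS event before the score. They rest on the nominal schedule and the plan's exponential rates. The rejection rates are illustrative only.

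The baseline half of the objective is sound. This is one secondary objective with no error rate or decision rule attached. A reader might extend the criticism to the primary result, but the Simon decision does not use CIRS.

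**What to change.** In 2.2(e) and 9.11.1:

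1. Name baseline CIRS as the only predictor of CR, TTF, FFP, PFS, OS and toxicity.
2. Report end-of-treatment CIRS as change from baseline, that is, as an outcome.
3. If its relation to later PFS or OS is wanted, start the clock at the date of that CIRS and include only patients alive and progression-free then.
4. Align the outcome list in 9.11.1 with 2.2(e), replacing the undefined DFS.

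The cost is wording; data collection does not change. The downside is that the landmark analysis has fewer patients: at the plan's rates, roughly 7 to 13 of 45 would drop out through earlier PFS events alone.

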3 SELECTION OF PATIENTS

3.1 Inclusion Criteria

- 3.1.1 Voluntary written informed consent before performance of any study-related procedure not part of normal medical care, with the understanding that consent may be withdrawn by the subject at any time without prejudice to future medical care.
- 3.1.2 ≥ 60 years old.
- 3.1.3 Previously untreated classical Hodgkin lymphoma (i.e., nodular sclerosis, mixed cellularity, lymphocyte depleted, lymphocyte-rich, and NOS). Nodular lymphocyte predominant Hodgkin lymphoma is not eligible.
- 3.1.4 Stage II, III, and IV disease by Ann Arbor classification.
- 3.1.5 ECOG performance status score of 0, 1, or 2.
- 3.1.6 Patients must have bi-dimensional measurable disease (as defined in section 6.1) within 60 days prior to starting treatment (at least 1.5 cm). Patients with non-measurable disease (defined in Section 6.1) in addition to measurable disease must have been assessed within 60 days prior to starting treatment.
- 3.1.7 Patients must have a bone marrow biopsy (bilateral preferred, unilateral acceptable) within 90 days prior to starting treatment.
- 3.1.8 Patients must have a MUGA or echocardiogram within 90 days prior to starting treatment and the ejection fraction must be $\geq 45\%$.
- 3.1.9 Adequate organ function including an ANC $> 1000/\text{mm}^3$, platelet count $> 75,000/\text{mm}^3$, creatinine < 2.5 mg/dl, and bilirubin < 3.0 mg/dl. Patients with documented marrow involvement by lymphoma at the time of registration are not required to meet the above hematologic parameters.
- 3.1.10 Patients must not have received prior chemotherapy or radiation therapy for the treatment of Hodgkin lymphoma.
- 3.1.11 Both females and males who have partners of childbearing potential must agree to use an effective contraceptive method during the study and for 30 days following the last dose of study drug.
- 3.1.12 Patients must sign the informed consent form before registration.

3.2 Inclusion of Women and Minorities.

- 3.2.1** Both men and women and members of all races and ethnic groups are eligible for this trial.

3.3 Exclusion criteria.

- 3.3.1** Previous treatment with SGN-35 or any other prior anti-CD30-based antibody therapy.
- 3.3.2** No currently active other (second) malignancy, other than non-melanoma skin cancers. Patients are not considered to have a “currently active” malignancy if they have completed anti-cancer therapy and are considered by their physicians to be at less than 30% risk of relapse.
- 3.3.3** Known cerebral/meningeal disease.
- 3.3.4** Any active systemic viral, bacterial, or fungal infection requiring IV treatment with antimicrobial therapy within 1 week prior to first dose.
- 3.3.5** Patients with known HBsAg positive HBV infection. Patients with prior history of Hepatitis B infection, but immune, with only IgG Hepatitis core antibody + (HBcAb +) must receive anti-viral prophylaxis (e.g., lamivudine 100mg po daily) for at least 1 week prior to cycle 1 and throughout induction and continuation therapy and for at least 6 months after the last SGN-35 dose. In addition, consultation with a hepatologist is recommended.
- 3.3.6** Patients with a known hypersensitivity to any excipient contained in the drug formulation.
- 3.3.7** Patients with dementia or an altered mental state that would preclude the understanding and rendering of informed consent.
- 3.3.8** Patients with a prior history of documented pancreatitis.
- 3.3.9** Patients with severe renal impairment (CrCL <30 mL/min). A calculated CrCl is acceptable.

